# 5.3.3 Precautionary Interventions

- 5.3.3.1 Induction of Hypothermia. Cold fluid infusion with up to 2 liters of chilled (4°C) IV fluids over approximately 30 minutes should be initiated after randomization. Once the intravascular cooling catheter is in place, goal temperature should be 35°C prior to dura opening, with maintenance at 33°C (32.5-33.5°C).
- 5.3.3.2 Procedure for Re-warming. At or shortly after the 48-hours of cooling, re-warming will be done very gradually. This will allow body temperature to increase no faster than 0.25°C every hour. This will be accomplished by setting the following method:
  - 1. Set the intravascular cooling catheter controls to automatic with the target temperature to be 37.0°C. (The machine itself should be set to 36.5°C to avoid overshooting the target temperature.)
  - 2. Set machine to rewarm at a rate of 0.25°C/hour. (The machine itself may need to be set to 0.1°C/hour to achieve this goal.)
  - 3. It takes 16-20 hours to rewarm a patient successfully and the unit must be on automatic at all times.
  - 4. Continue use of room temperature ventilated air until 37.0°C is reached.
    - a. If the ICP is elevated (>20mmHg) do not rewarm at 48 hours, may keep the subject cool up to 5 days.
    - b. If the ICP elevates as rewarming hold the temperature where it is and add additional standard measures for treating elevated ICP. If no response to treatments in 6 hours and ICP is ≥25mmHg, re-cool to 33°C.
    - c. Goal is to have the subject re-warmed within 5 days.

#### 8 Hours Prior to Re-warming:

- 1. Stop all potassium and magnesium administration 8 hours before the start of rewarming to reduce the likelihood of hyperkalemia and hyper-magnesium during rewarming.
- 2. Determine fluid balance 8 hours prior to the start of re-warming:
  - a. If <0 cc, administer additional intravenous fluid (colloid, crystalloid, or a combination) to achieve a positive balance.
  - b. Administer 1000cc volume load to all subjects who have a cumulative fluid balance of 0 999cc.
  - c. It is important to ensure that there is adequate circulating blood volume (Hgb>8 grams and Hct > 30%) when the patient begins to vasodilate with re-warming.

#### **During re-warming:**

- 1. Monitor bladder temperature, ICP, MAP, and CPP hourly.
- 2. If ICP increases above 20mmHg, rewarming will be suspended per protocol.

- 3. Maintain CPP between 50 and 70 mmHg using volume expansion and vasopressors, as needed. If MAP <90 mm Hg, start a vasopressor agent and evaluate response, additional agents may be used if necessary.
- 4. The ICP monitor must remain in place for at least 24 hours after re-warming is complete, (even if the ICP's are within normal limits) in order to detect rebound increase in ICP after re- warming.

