#### 5. STUDY INTERVENTIONS

#### 5.1 Interventions, Administration, and Duration

This is a pragmatic study; patients will be treated with standard care as established at each enrolling center. All of the enrolling sites utilize Brain Trauma Foundation Guidelines as foundation for delivery of care(40). Intravascular cooling catheters may be placed in the emergency room, the operating room or neurotrauma intensive care unit (NTICU). Patients randomized to hypothermia will be rapidly cooled to 35°C before opening the dura and then maintained at 33°C±0.5°C for a minimum of 48 hours and a maximum of 5 days. After evacuation of SDH all patients will be cared for in the ICU by teams experienced in hypothermia and the management of TBI.

Intravascular cooling will be provided by CoolGard 3000 or Thermogard XP which use an intravenous central catheter circulating cooled saline in a closed loop system. These devices

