# 6.2.2 On-Study/On-Intervention Evaluations

Within 6 hours of injury (T1)

Blood (and CSF if available) should be collected

Up to 2 liters IV fluid administered

Placement of intravascular catheter

Cooling to 35°C for hypothermia arm; 37°C for normothermia

Opening of dura (followed by evacuation of SDH)

Adverse events monitored

• >6 to 48 hours post-injury (T2)

Following hematoma evacuation and hemostasis ECoG Electrode strips should be placed

Upon admission to the ICU, following surgery, the leads from the ECoG electrode strip will be connected to an EEG amplifier. External ground and reference electrodes will be placed and continuous ECoG recordings will then commence.

Repeat head CT as indicated for clinical care

Temperature maintenance of 33°C for hypothermia arm; 37°C for normothermia arm

Blood (and CSF if available) should be collected

Adverse events monitored

>48 hours to 5 days

Rewarming initiated according to rewarming protocol (37°C for normothermia arm)

Continuous ECoG monitoring will be performed for at least the same duration as ICP monitoring. In patients randomized to hypothermia, this is

until at least 24 hours after re-warming is complete. In normothermia patients, patients will be monitored a minimum of 96 hours, and longer if continued ICP monitoring is clinically indicated. When monitoring is complete, the electrode strip will be removed at the bedside under sterile conditions, as is performed for standard-of-care intracranial devices.

Adverse events monitored

(±0.5°C for all temperatures)

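### Rewarming item 3: assuming CPP = MAP − ICP, the MAP <90 mmHg vasopressor trigger fires at every on-target CPP when ICP is below 20, and at low ICP above the target too

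*Combined protocol and SAP*

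**What the plan says.** The instruction is item 3 of the During re-warming list, under section 5.3.3.2 of the protocol: "Maintain CPP between 50 and 70 mmHg using volume expansion and vasopressors, as needed. If MAP <90 mm Hg, start a vasopressor agent". It continues: "start a vasopressor agent and evaluate response, additional agents may be used if necessary". The qualifier about need belongs to the CPP sentence. The MAP sentence has no condition on CPP or ICP.

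Two other items set the ICP range in which rewarming goes on. Item 4a of the procedure says "If the ICP is elevated (>20mmHg) do not rewarm at 48 hours", and item 2 of the During re-warming list says "If ICP increases above 20mmHg, rewarming will be suspended per protocol". Item 1 of that list makes all the pressures available together: "Monitor bladder temperature, ICP, MAP, and CPP hourly".

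The pre-rewarming steps ask for adequate circulating volume "when the patient begins to vasodilate with re-warming", so a fall in vascular tone is expected. On general care, section 5.1 says "All of the enrolling sites utilize Brain Trauma Foundation Guidelines as foundation for delivery of care", and section 6 refers management to each institution's standard care. Neither gives a MAP or CPP number. The protocol does not define CPP, give a reference level for MAP or ICP, or say which of the two limits in item 3 comes first.

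**The concern.** A CPP range and a MAP threshold in the same item should be compatible at the ICP values where the item is used. If the threshold lies above the MAP values that produce an on-target CPP, staff who follow the text start a vasopressor in a patient whose perfusion pressure already meets the protocol's own target. At low ICP they would do so in a patient already above it. Sites could also settle the matter differently, some working to CPP and others to MAP.

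Controlled rewarming belongs to the hypothermia strategy (section 6.2.2 keeps the normothermia arm at 37°C), and the protocol sets no MAP or CPP rule for the normothermia arm. Any extra vasopressor starts would therefore occur in the hypothermia arm.

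**Working it through.** The plan gives no calculated figure to reproduce. The check is whether the limits fit together.

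**Inputs from the protocol:** CPP target 50–70 mmHg and trigger MAP <90 mmHg (During re-warming, item 3); rewarming not started, and suspended, at ICP above 20 mmHg (5.3.3.2 item 4a; During re-warming, item 2).

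**Assumption:** CPP = MAP − ICP, with both pressures at a shared reference level.

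**Step 1. Shared reference level.** On-target MAP runs from 50 + ICP to 70 + ICP. The trigger MAP <90 is the same as CPP < 90 − ICP.

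| ICP | MAP giving CPP 50–70 | Trigger fires at CPP below | On-target whole-mmHg values that fire | Above-target CPP that fires |
|---|---|---|---|---|
| 5 | 55–75 | 85 | 21 of 21 | 71–84 |
| 10 | 60–80 | 80 | 21 of 21 | 71–79 |
| 15 | 65–85 | 75 | 21 of 21 | 71–74 |
| 20 | 70–90 | 70 | 20 of 21 | none |

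The top of the on-target MAP range, 70 + ICP, reaches 90 only at ICP 20. Below that, no reading is both on target and clear of the trigger. At ICP 20 the single exception is MAP 90, CPP 70.

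**Step 2. Different reference levels.** Suppose the MAP used for the trigger reads d mmHg higher than the pressure used to compute CPP, so that CPP = MAP − d − ICP. The trigger becomes CPP < 90 − ICP − d, and the share of the 50–70 range that meets it is (40 − ICP − d)/20, bounded between 0 and 1.

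- With d = 15: (40 − 10 − 15)/20 = 75% at ICP 10, 50% at ICP 15 and 25% at ICP 20.
- Firing above CPP 70 needs 90 − ICP − d > 70, so it stops once ICP + d reaches 20.
- The overlap with the target vanishes only when d is at least 40 − ICP: 30 mmHg at ICP 10, 25 at ICP 15, 20 at ICP 20.

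**Step 3. Summary over a grid.** Over whole-mmHg pairs with ICP 5–20 and CPP 50–70 (16 × 21 = 336), the pairs that meet the trigger number 335 for d = 0, 315 (94%) for d = 5, 270 (80%) for d = 10 and 200 (60%) for d = 15. Each pair counts equally and the lower ICP limit of 5 is chosen for illustration. Extending the grid down to ICP 0 gives 440 of 441 for d = 0.

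**Step 4. ICP above 20.** With d = 0, MAP 90 corresponds to CPP 65 at ICP 25, 60 at ICP 30 and 50 at ICP 40. The threshold fits the CPP range better there, but rewarming is then on hold.

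**The case against.** The strongest reply is that the two sentences can both be obeyed. Item 3 does not make MAP 90 a target. It says to start an agent and evaluate the response, so a clinician can start one and titrate to keep CPP at 50–70. Since vasodilation is expected, an early trigger may have been intended. This stands in part: a reader might infer a flat logical contradiction, and the text does not support that. But the protocol nowhere says an early trigger is meant, and that intent does not explain starting a vasopressor when CPP is already above 70.

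Second, item 4b of 5.3.3.2 has temperature held and ICP treated when ICP rises during rewarming, and nothing says item 3 lapses during that hold. That is fair, and step 4 shows the threshold is more sensible there. It leaves the overlap at ICP of 20 or less where it was.

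Third, sites follow common guidelines and local standard care. These references are general and supply no number that reconciles the limits, whereas rewarming is set out in numbered steps.

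Fourth, haemodynamic support during rewarming is arguably part of the strategy under test. This also stands. A reader might infer from the one-arm exposure that the GOSE comparison is biased. The documents do not show that.

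**Conclusion.** As a clinical instruction, item 3 is wrong as written, and the issue is one of patient safety. With CPP = MAP − ICP at a shared reference level, the trigger fires at every on-target CPP for any ICP below 20. It also fires above the target at low ICP, for example up to CPP 84 at ICP 5. A plausible offset shrinks the overlap without removing it: at 15 mmHg a quarter of the target range still meets the trigger at ICP 20.

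A reader might take 335 of 336 as the proportion of patients who would get an unneeded vasopressor. It is not. The documents give no distribution of ICP, MAP or CPP, so the figures describe combinations of readings, and the number of patients affected is unknown. No effect on sample size, power, error rates or the primary comparison is shown. The documents also do not settle whether 90 was meant for a different pressure.

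**What to change.** Replace the MAP <90 trigger with one tied to CPP: begin a vasopressor when CPP is under 50 mmHg or falling toward it, and titrate to 50–70. Keep a separate MAP floor no lower than 60 mmHg, the level that section 4.2 treats as haemodynamic instability when MAP stays below it for 30 minutes.

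The amendment should not say that CPP overrides any MAP value. At ICP 5, CPP 50–54 corresponds to MAP 55–59, below that level. With a floor of 60, the MAP rule would fire at CPP below 60 − ICP, which is below 55 at ICP 5 and below 50 at ICP 10, so it would never fire above the target.

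Alternatively, the clinical leads substitute the pressure variable and value they intended, provided it is consistent with CPP 50–70 at ICP of 20 or less. Either way, state the reference level for MAP and ICP and which limit takes priority.

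The cost is a one-line amendment and a site memo, with the clinical leads confirming the value. No new data are needed, because MAP, ICP and CPP are already recorded hourly during rewarming.

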#### 5.4 Adherence Assessment

Compliance with the study intervention will be assessed by monitoring temperature data. Analysis will be performed on time to reach goal temperature, duration of cooling, and temperature ranges for each group during the intervention period.

# 6. CLINICAL AND LABORATORY EVALUATIONS

Management is per standard care at each institution. All centers practice in accordance with Brain Trauma Foundation Guidelines.

# 6.1 Schedule of Evaluations (Table 1.)

Evaluation	Screening (<5hrs of injury)	Entry T1 <6hrs of injury	7 to 48hrs T2	>48 hrs-5d	5-14d T3	4-6 wk	6mons+/-3 weeks
Documentation of Injury (Head CT/MRI)	SOC		SOC				
Medical/Treatment History	SOC						
Clinical Assessment	SOC		Х	Х	Х		
Physical Exam	SOC						
Informed Consent	Per center	approved process			•		
Hypothermia (Control)			Х	Х			
Dura Opening/SDH Evacuation		SOC					
Brain Activity Monitoring			Х	Х	Х		
Rewarming				Х			
Hematology	SOC		SOC		SOC		
Chemistry	SOC		SOC		soc		
Pregnancy Testing	SOC						
Stored Plasma/CSF		Х	Х		Х		
Adherence Assessments			Х	Х			
Adverse Event Assessments		Х	Х	Х	Х	Х	Х
Outcome (DRS; GOSE)						Х	Х

SOC=per standard care

# 6.2 Timing of Evaluations

#### 6.2.1 Pre-Randomization Evaluations

These evaluations occur prior to the subject receiving any study interventions.

#### Screening

Subjects enrolled in this study will have a goal of SDH evacuation within 6 hours of injury. Screening must be completed to allow time for catheter placement and cooling down to 35°C prior to opening of the dura. All screening evaluations are part of routine patient management for TBI patients.

#### Pre-Entry

T1 blood draw may be taken with routine blood draw, processed and held (discarded if subject is not enrolled).

#### **Entry**

Randomization should occur immediately upon confirmation of enrollment criteria. Initiation of study intervention should commence immediately after randomization.

# 6.2.2 On-Study/On-Intervention Evaluations

Within 6 hours of injury (T1)

Blood (and CSF if available) should be collected

Up to 2 liters IV fluid administered

Placement of intravascular catheter

Cooling to 35°C for hypothermia arm; 37°C for normothermia

Opening of dura (followed by evacuation of SDH)

Adverse events monitored

• >6 to 48 hours post-injury (T2)

Following hematoma evacuation and hemostasis ECoG Electrode strips should be placed

Upon admission to the ICU, following surgery, the leads from the ECoG electrode strip will be connected to an EEG amplifier. External ground and reference electrodes will be placed and continuous ECoG recordings will then commence.

Repeat head CT as indicated for clinical care

Temperature maintenance of 33°C for hypothermia arm; 37°C for normothermia arm

Blood (and CSF if available) should be collected

Adverse events monitored

>48 hours to 5 days

Rewarming initiated according to rewarming protocol (37°C for normothermia arm)

Continuous ECoG monitoring will be performed for at least the same duration as ICP monitoring. In patients randomized to hypothermia, this is

until at least 24 hours after re-warming is complete. In normothermia patients, patients will be monitored a minimum of 96 hours, and longer if continued ICP monitoring is clinically indicated. When monitoring is complete, the electrode strip will be removed at the bedside under sterile conditions, as is performed for standard-of-care intracranial devices.

Adverse events monitored

(±0.5°C for all temperatures)

#### 6.2.3 Intervention Discontinuation Evaluations

Subjects who prematurely discontinue study intervention will complete controlled rewarming per protocol for patient safety. This trial follows an intention-to-treat design, subjects who discontinue intervention will continue to be followed and evaluated on study. Efforts will be made to retain such subjects on study for the 4-6 week and 6 month outcome assessments. Once a subject discontinues from the study intervention they will not receive continued intravascular hypothermia.

#### 6.2.4 On Study/Off-Intervention Evaluations

• 5-14 days (T3)

Blood (and CSF if available) should be collected Adverse events monitored

4-6 weeks

**DRS** 

**GOSE** 

Adverse events monitoring

• 4 weeks – 6 months

Follow-up on adverse events as necessary
Maintain subject contact (Phone calls/emails as necessary)

- i. Final On-Study Evaluations
- 6 months±3 weeks

DRS

**GOSE** 

Adverse events monitoring

# 6.3 Special Instructions and Definitions of Evaluations

**6.3.1** Informed Consent. Patients will be randomized within 5 hours of arrival to the ED. If a patient arrives in the ED with family members present or before craniotomy is performed, then a prospective informed consent will be obtained. In Houston, Cincinnati, Atlanta and Pittsburgh, every attempt will be made to identify family as soon as possible but randomization will not be delayed for this purpose. If no family is identified the study team will continue to make every attempt to locate the family throughout the patient's hospital stay. In Miami, exception from informed consent is not permitted according to state law; consent will be obtained per state regulations. The Japanese sites will obtain consent per their local regulations.

Centers must comply with Federal standards for community consultation and notification. In particular, community consultation as directed by each site's institutional review board. (Please see attached plan.) For those patients enrolled and randomized under waiver, a study team member must meet with the family as soon as possible and explain the study in detail to them. The Legally Authorized Representative must be identified and permission to continue the study must be requested. Should permission be denied then those patients assigned to hypothermia will be gradually re-warmed. If the patient has been cooled to 33°C then the re-warming should be performed per protocol.

In Randomized patients, permission must be obtained from the Legally Authorized Representative or the patient to use the data collected for that patient. This will be documented on the appropriate HIPPA forms.

- **6.3.2 Documentation of Traumatic Brain Injury requiring Emergent Craniotomy.** Subdural hematoma will be documented by standard of care brain imaging (head CT or MRI)
- **6.3.3 Medical History.** Medical history will be obtained from family member if available.
- **6.3.4 Concomitant Treatments.** Documentation of therapeutic intensity level (TIL) and concomitant treatments per the Common Data Elements (CDE) forms will be collected.
- **6.3.5 Study Intervention Modifications.** Any modification to hypothermia/normothermia will be documented with rationale.
- **6.3.6 Clinical Assessments.** A targeted physical exam is completed on presentation to the emergency department. Clinical events should be recorded on the case report forms (CRFs) and will include adverse events, temperature, ICP, MAP, pupil size and reactivity, hematoma size, midline shift, GCS, GOSE, and DRS. GOSE and DRS will be assessed by evaluator who is unaware of (blind) the study group assignment.
- **6.3.7 Laboratory Evaluations.** Baseline standard care laboratory studies will be recorded utilizing the CDE data elements, thereafter relevant abnormal laboratory studies during the treatment period will be evaluated against the USDHHS Common Terminology Criteria for Adverse Events V4.0 USDHHS criteria for adverse events(46). Those with a grade >3 will be documented.
- **6.3.8 Other Laboratory Studies**. Plasma for biomarker analysis: Blood will be withdrawn from existing lines or by venipuncture and collected into two pink top K2EDTA 6ml (plasma) Vacutainers per time point (36 ml). The samples will be placed on ice and will be centrifuged at 1,459 X g for 10min at 4°C. The supernatant solution will be removed and centrifuged at 1,459 X g for 10min at 4°C to generate platelet-poor plasma. Plasma will be divided into aliquots and frozen at -80°C until needed. For those subjects providing consent, any residual sample and buffy coat will be frozen at -80°C for future study.
- CSF for biomarker analysis: Patients with a ventriculostomy drain will have 1-5 ml of CSF sampled from the receptacle at each of 3 time points. The receptacle will be emptied into the collection bag (the volume will be noted in the nursing notes) to start with an empty receptacle, several drops of CSF will then be allowed to drip into the chamber. The drain will be re- clamped; the chamber port will be cleaned with chlorhexidine as per hospital specifications and

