#### 7. **MANAGEMENT OF ADVERSE EXPERIENCES**

Adverse events will be graded according to the USDHHS Common Terminology Criteria for Adverse Events V4.0 (USDHHS, Table 2) and summarized according to body system. Primary focus for analysis will be on 6-month mortality rate, incidence of pneumonia, incidence of DVT/PE, incidence of bleeding and incidence of arrhythmia. For the purpose of safety monitoring, adverse events in the table below of Grade 3 or higher will be classified as "Important AEs" or selected AEs of interest.

Table 2. Selected AEs	Table 2. Selected AEs from USDHHS Common Terminology Criteria for Adverse Events V4.0 USDHHS									
Adverse Event	Grade 1	Grade 2	Grade 3	Grade 4	Grade 5					
Sinus Bradycardia	Asymptomatic, intervention not indicated	Symptomatic, medical intervention indicated	Severe, medically significant, medical intervention indicated	Life-threatening consequences; urgent intervention indicated	Death					
Supraventricular tachycardia	Asymptomatic, intervention not indicated	Non-urgent medical intervention indicated	Medical intervention indicated	Life-threatening consequences; hemodynamic compromise; urgent intervention indicated	Death					
Ventricular arrhythmia	Asymptomatic, intervention not indicated	Non-urgent medical intervention indicated	Medical intervention indicated	Life-threatening consequences; hemodynamic compromise; urgent intervention indicated	Death					
Thromboembolic event	Venous thrombosis (e.g., superficial thrombosis)	Venous thrombosis (e.g., uncomplicated deep vein thrombosis),	Thrombosis (e.g., uncomplicated pulmonary embolism [venous],	Life-threatening (e.g., pulmonary embolism, cerebrovascular event, arterial	Death					

			1	02/23/	2018                                    
		medical intervention indicated	nonembolic cardiac mural [arterial] thrombus), medical intervention indicated	insufficiency); hemodynamic or neurologic instability; urgent intervention indicated	
Pneumonia			Dyspnea and pneumonia symptoms (e.g., aspiration pneumonia); hospitalization indicated; unable to aliment orally	Life-threatening respiratory or hemodynamic compromise; intubation or urgent intervention indicated	Death

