#### 9.5.3 Interim Analysis on Safety.

The probability of selected adverse events of interest (defined in Section 7), and separately of deaths, will be monitored based on a beta-binomial model. Enrollment will be placed on hold pending DSMB review if the proportion of selected adverse events of interest in the treatment arm is too high in comparison to the control arm or if the proportion of deaths in the treatment arm is too high in comparison to the control arm. The selected adverse events of interest will also include patient deaths.

The DSMB will perform a more detailed review of the selected AEs of interest to determine if the study should continue. In particular, enrollment will be placed on hold if,  $Pr(p1 > p0 \mid data) > 0.98 \text{ OR } Pr(pdeath1 > pdeath0 \mid data) > 0.98$ ,

where p1 and p0 are the proportion of patients with selected AEs of interest in the hypothermia and control arms, respectively, and pdeath1 and pdeath0 are the proportion of patients that died. The prior distributions for p1, p0, pdeath1, and pdeath0 are independent, ran-informative Beta (1, 1). The 0.98 thresholds were selected to adjust partially account for the multiple interim analyses scheduled to occur. We will start to perform the interim analysis on safety for the first 10 patients in each arm randomized, and then other interim analyses will be carried out every 10 patients in both arms (20 patients). The operating characteristics for the stopping rules under various scenarios are summarized in Table 5, with results based on 10000 simulations.

Table 7. summarized the simulation results with interim analyses for safety every 20 patients randomized, assuming there will be 120 patients (60 per arm).

Table 7

Scenario	Selected AEs of	Death		
	Interest	Interest proportions		
	proportions		% trials with at least one	Mean number
	(Control, Treatment)	(Control, Treatment)	hold for safety evaluation	of pts
1	(0.25, 0.10)	(0.125), 0)	0.08%	120
2	(0.25, 0.15)	(0.125, 0.025)	0.4%	120
3	(0.25, 0.25)	(0.125, 0.125)	7.5%	115
4	(0.20, 0.30)	(0.10, 0.20)	39.7%	96
5	(0.20, 0.40)	(0.10, 0.30)	81.1%	66
6	(0.20, 0.50)	(0.10, 0.40)	97.4%	45
7	(0.20, 0.60)	(0.10, 0.50)	99.8%	33

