#### 10.4 ADVERSE EVENT REPORTING

Complications due to hypothermia include bradycardia or arrhythmias, a reduced immune system, blood clotting, increased insulin resistance, and electrolytes to shift, causing potassium levels to appear low because of increased absorption into cells(33;49). However, patients treated with intravascular cooling do not experience the complications of skin rashes, burns and skin death(33). Intravascular cooling catheters function as central venous catheters and contain working ports that facilitate routine critical care such as administering drugs and fluids and drawing blood.

Safety assessments will consist of monitoring and reporting adverse events (AEs), selected adverse events of interest, and serious adverse events (SAEs), both anticipated and unanticipated. An Adverse Event is any undesirable and unintended, although not necessarily unexpected, event occurring in human subjects as a result of (a) the interventions and interactions used in the research; or (b) the collection of identifiable private information under the research. A Serious adverse event is an adverse event that led to death, or to serious deterioration in the health of the subject, that resulted in death, was life-threatening, required hospitalization (initial or prolonged), resulted in disability or permanent damage, congenital anomaly/birth defect, required intervention to prevent permanent impairment or damage, or other serious events (Important Medical Events). NOTE: Planned hospitalization for a preexisting condition, or a procedure required, without serious deterioration in health, is not considered a serious adverse event. An unanticipated adverse device effect as defined by FDA regulations, 2CFR 812.3(s) is any serious adverse effect on health or safety or any life- threatening problem or death caused by, or associated with, a device, if that effect, problem, or death was not previously identified in nature, severity, or degree of incidence in the investigational plan or application (including a supplementary plan or application), or any other unanticipated serious problem associated with a device that relates to the rights, safety, or welfare of subjects.

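### Section 6.3.7 requires post-baseline laboratory abnormalities to be documented only above Grade 3, so Grade 3 electrolyte, glucose and coagulation-test results are not captured systematically

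*Combined protocol and SAP*

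**What the plan says.** Section 6.3.7 (Laboratory Evaluations) has three parts:

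- At baseline, "Baseline standard care laboratory studies will be recorded utilizing the CDE data elements".
- After baseline, "thereafter relevant abnormal laboratory studies during the treatment period will be evaluated against the USDHHS Common Terminology Criteria for Adverse Events V4.0".
- The documentation threshold for those later results is "Those with a grade >3 will be documented".

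Section 7 sets a different threshold for a different set of data. It applies to "adverse events in the table below of Grade 3 or higher", which are classed as important or selected events. The safety analysis is centred on clinical endpoints: "Primary focus for analysis will be on 6-month mortality rate, incidence of pneumonia, incidence of DVT/PE, incidence of bleeding and incidence of arrhythmia".

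Section 6.3.6 places adverse events on the case report form, and Section 9.5 reports them by type, frequency and severity. Neither gives a minimum grade. Section 10.4 defines an adverse event as one that arises from the research interventions or from the collection of private information.

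The protocol expects laboratory disturbance from the intervention. Sections 2.2 and 11.4 list electrolyte disorders and hyperglycemia among the risks of hypothermia. Section 10.4 adds clotting, insulin resistance and electrolyte shifts, the last "causing potassium levels to appear low because of increased absorption into cells". The re-warming procedure in Section 5.3.3 contains a step meant to limit high potassium and magnesium.

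**The concern.** Safety of intravascular cooling is a stated secondary objective, and adverse events are to be tabulated by severity. Electrolyte and glucose disturbances are among the effects that the protocol names as risks of cooling or re-warming. A documentation threshold that starts at Grade 4 leaves out a whole grade of these abnormalities, and no reason is given for starting there.

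What is at stake is the laboratory part of the severity comparison between arms. If Grade 3 results reach the database only when someone chooses to report them, the comparison mixes the true frequency with reporting behaviour. In this trial the staff who deliver the temperature target know which arm the patient is in.

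**Working it through.** No sample size, power or event count is involved, so the check is a comparison of rules and their scope.

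**Step 1: the thresholds.** Table 2 shows a five-grade integer scale. On it, greater than 3 gives {4, 5}, and 3 or higher gives {3, 4, 5}. The two differ by exactly Grade 3.

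**Step 2: the scope of each recording route.**

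| Route | Data covered | Grade needed | Filter |
|---|---|---|---|
| 6.3.7, baseline | Standard-care laboratory studies | Any | None |
| 6.3.7, treatment period | Abnormal laboratory studies | 4–5 | Must be relevant |
| Section 7, Table 2 | Listed clinical events | 3–5 | Must be in the table |
| 6.3.6, 9.5, 10.4 | Adverse events generally | None stated | Must meet the Section 10.4 definition |

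**Step 3: does Table 2 cover laboratory results?** Its rows are sinus bradycardia, supraventricular tachycardia, ventricular arrhythmia, thromboembolic event, pneumonia, pulmonary edema, bleeding, intraoperative hemorrhage, culture-positive infection, device-related infection and death. None is an electrolyte, glucose or coagulation-test term. Section 7 and Section 6.3.7 therefore apply to different data, and Table 2 is no backstop for laboratory results.

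**Step 4: what is left for a Grade 3 laboratory result?** Only the last route in the table. Under Section 10.4 it depends on the result being judged to arise from the research. Sections 6.3.6 and 9.2.1 describe only the GOSE and DRS evaluators as blind. Staff running 33°C or 37°C targets cannot be.

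**Step 5: effect on the comparison.** Let q_t and q_c be the true proportions of patients with a Grade 3 laboratory abnormality in the hypothermia and control arms. Let r_t and r_c be the chances that such an abnormality is recorded as an adverse event.

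- True difference: q_t − q_c.
- Expected recorded difference: r_t·q_t − r_c·q_c.
- Equal recording (r_t = r_c = r): the difference shrinks to r(q_t − q_c).
- Equal true rates (q_t = q_c = q): a spurious difference of q(r_t − r_c) appears.

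The documents give none of q_t, q_c, r_t or r_c, so neither the size nor the direction can be computed.

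**Step 6: what does not depend on Section 6.3.7.** The hold rule in Section 9.5.3 uses deaths and selected events, "where p1 and p0 are the proportion of patients with selected AEs of interest in the hypothermia and control arms". Those events come from Table 2, so the rule and Tables 7 and 8 are the same under either threshold. The primary test uses GOSE alone.

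**The case against.** The strongest case on the other side has four parts.

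1. *There is no contradiction with Section 7.* This stands. A reader might infer that the protocol sets two thresholds for the same data. It does not, because the Section 7 rule is confined to Table 2. Raising Grade 3 laboratory results into Section 6.3.7 would not make them important events under Section 7.

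2. *Grade 3 results are not lost.* This also stands. A reader might infer that they never reach the case report form. Section 6.3.7 sets a minimum for documentation and does not bar other recording. Adverse events are collected from entry to 6 months with no grade floor. Section 10.4 also assesses relatedness as a separate step, so sites may in practice record events they think unrelated. Even so, deciding that a laboratory value is an adverse event remains a judgement made with the arm known. Being standard-care results, the values could in principle be retrieved from the hospital record later.

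3. *The clinical consequences are captured anyway.* Largely true: arrhythmia, bleeding and thromboembolism at Grade 3 or higher are in Table 2. That does not give a laboratory severity comparison.

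4. *A high threshold is a reasonable economy in a pragmatic trial.* It could be, but the protocol does not say so. It is equally possible that ≥3 was meant. The sign ≥ is used elsewhere (the re-warming procedure in Section 5.3.3), so a slip cannot be presumed, and neither can intent.

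A reader might also infer that the rule makes hypothermia look safer. The documents do not support a direction. The threshold is the same in both arms, and step 5 of the working shows that differential recording could push the difference either way.

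**Conclusion.** The point holds as a small, correctable gap. As written, Section 6.3.7 does not require Grade 3 electrolyte, glucose or coagulation-test abnormalities in the treatment period to be documented, and no other rule in the protocol captures them systematically. Their recording rests on attribution by unblinded site staff, so the planned comparison by severity would be incomplete for this grade and open to bias.

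The number of events cannot be derived from the documents. Nothing changes in the primary analysis, the safety hold rule or its simulated operating characteristics.

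The conclusion rests on three readings: that the sign in Section 6.3.7 is meant strictly; that the Section 10.4 definition is what sites apply when deciding what to record; and that treating staff know the assignment. The last follows from the nature of the intervention and is not stated outright. If ≥3 was intended, the point reduces to correcting the text, which is still needed because sites follow what is written.

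**What to change.** First confirm whether ≥3 was intended. Then amend Section 6.3.7 so that laboratory abnormalities of Grade 3 or higher in the treatment period are documented in both arms, irrespective of whether anyone attributes them to the research. Because the section applies only to relevant abnormal results, state that electrolyte, glucose and coagulation tests count as relevant. If Grades 4 and 5 alone were intended, say so, give the reason, and limit the laboratory safety conclusions to those grades.

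The cost is one amended sentence and somewhat more data entry. No extra tests are needed: Table 1 marks hematology and chemistry as standard care. It has no separate coagulation row, so for those tests the amendment would capture whatever standard care produces. No change to patient management, sample size or any analysis threshold follows.
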